3.3.2. Secondary Study Endpoints

1. Time to complete wound closure
2. Change in wound size over time
3. Incidence of reoccurrence
4. Incidence of amputation
5. Incidence of adverse events
6. Quality of Life – Pain, Mood and Function
7. Health Economic Analysis

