7.1.2. Secondary Efficacy Assessments

Time to complete wound closure

The time (in days) from first treatment at baseline of the ulcer until it closes completely will be recorded.

Change in wound size over time

Ulcer size over time will be assessed from the digital photographs of the ulcer taken at each visit.

Incidence of recurrence

Recurrence is identified as an interruption in the epithelium following complete healing of the index ulcer. If the subject does have a recurrence, this will be documented and the re-opened ulcer will be measured and recorded

Incidence of Amputation

All amputations will be recorded. The investigator will judge whether the amputation was done because of the index ulcer or for different reasons.

Incidence of adverse events and device effects

Quality of Life

Pain - A Visual Analogue Scale will be used to determine pain levels.

Mood and Function - The Cardiff Wound Impact Schedule (CWIS) assesses levels of mood and function and is the tool used to determine Quality of Life (Appendix I). (Subjects in countries where the CWIS has not been validated will be debriefed on its use at the end of the study).

Economic Analysis

Economic assessments will be determined from the Euroqol-5D (EQ-5D), subject diary and

medical records documenting dressing changes, time, location and healthcare professional assistance and management (Appendix I).

Cost effectiveness will be determined by examining the difference in the number of healed ulcers in relation to the difference in cost in each randomized group

Incremental cost per additional ulcer healed=
$$\frac{\text{Cost of treatment (TWO) - Cost treatment (Control)}}{\text{Healed ulcers (TWO) - Healed ulcers (Control)}}$$

Cost Utility will be determined by examining the difference in Quality Adjusted Life Years (QALYs) associated with the different treatment regimens and their associated costs. Health utilities will be derived from the EQ-5D tool and used to calculate QALYs in each group. This will be related to overall treatment costs using the following formula

Incremental cost per QALY =
$$\frac{\text{Cost of treatment (TWO)-cost of treatment (control)}}{\text{QALY (TWO) - QALY(control)}}$$

See 7.2 Safety Endpoints

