- 12) Blood sample taken to obtain values for (**visit 12 only**):
 - Electrolytes
 - Creatinine
 - HbA1c, blood glucose
 - WBC
 - Albumin and pre-albumin (where available)
 - CBC
 - C-reactive protein
- 13) EQ-5D) (week 4, 8 and 12 only)
- 14) Education on diabetes management and foot care and off-loading boot/CROW boot
- 15) Dispense study dressings and diary card
- 16) Device competency assessment (completed in subject's home or equivalent. Week 4 and 8 only)

8.2.5 *Punch biopsies*

Punch biopsies may be taken at baseline and 4 weeks for up to 20 subjects enrolled in the study at selected centers. These subjects will have specifically agreed to this procedure on their Informed Consent Form.

The biopsies will be taken utilizing a standard 4 mm dermal punch biopsy kit and will be taken following routine debridement of the wounds to avoid collection of dead necrotic tissue. Prior to biopsy collection, the wound bed is prepared with local antiseptics. As per subject request, local anesthesia is administered. This is not standard because most subjects in this study will be insensate in the area of the wound.

In addition it is important to have some tissue samples without local anesthetic to determine whether the use of anesthetic agents impacts the molecular studies planned with the biopsy. Biopsies will be taken from the wound edge and from the center of the wound.

Samples will be collected, packed and transported per the procedure outlined by the testing laboratory instructions. The samples will be transported from clinic to the testing laboratory in properly secured biohazard-safe containers under appropriate temperature conditions.

The samples will be analyzed histologically for signs of infection, collagen and neo-angiogenesis. Additional immune-histochemical analyses for such values as VEG-F and matrix metalloproteinases (MMPs) are also envisioned.

8.2.6 *Premature Withdrawal of a Subject from the Trial*

Subjects are free to withdraw from the trial at any time without penalty or prejudice to their further treatment. Subjects may stop the trial treatment for any reason.

All subjects should be invited to do the End of Trial Visit to complete a final assessment, including wound status, complete quality of life questionnaire, etc.

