Subjects whose index ulcers are confirmed as closed will enter into the follow-up phase and will be terminated from further treatment with TWO2 therapy or Control therapy. Subjects will be encouraged to continue to wear the standard off-loading boot/CROW boot during the follow-up phase.

8.2.8 12 Week Follow up

All subjects will be reviewed and followed up 12 weeks after “wound closure” or the 12-week “end of treatment phase”, whichever is sooner +/- 2 weeks. Data for 12 week follow up analysis will be collected per the subject’s preference by telephone or in the clinic if attending a routine visit for wound care. Index ulcers not yet healed, will continue to be treated with best available therapy as determined by the treating medical provider.

The following assessments will be performed on all subjects:

- 1) Verify Informed Consent
- 2) Record adverse events
- 3) Record changes in concomitant medication
- 4) Quality of Life Assessment using CWIS
- 5) Pain Assessment using the Visual Numerical Rating Scale (where possible, if applicable)
- 6) Digital Photograph of the open index ulcer
- 7) Health Economic Assessment (including EQ-5D)
- 8) Education on diabetes management (and foot care/off-loading when indicated)

8.2.9 38 Week Follow up

The 38 week follow up will take place 26 weeks +/- 2 weeks from the time of the last study visit (12 week follow up). Data for 38 week follow up analysis will be collected per the subject’s preference by telephone or in the clinic if attending a routine visit for wound care. Index ulcers not yet healed, will continue with best available therapy as determined by the treating medical provider.

- 1) Verify Informed Consent
- 2) Record adverse events
- 3) Record changes in concomitant medication
- 4) Quality of Life Assessment using CWIS
- 5) Pain Assessment using the Visual Numerical Rating Scale (where possible, if applicable)
- 6) Digital Photograph of the open index ulcer (where possible)
- 7) Health Economic Assessment (including EQ-5D)
- 8) Education on diabetes management (and foot care/off-loading when indicated)
- 9) Debriefing of subjects where CWIS not previously validated

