9.4 Secondary outcome analyses

9.4.1 Time to complete wound closure

The analysis will use the Cox proportional hazards model to determine time to event (healing). Subjects who withdraw from treatment will be entered into the analysis and censored at the time they withdraw from the trial or are lost to follow up. The analysis will consider covariates that might influence the outcome in the trial. Factors considered potentially important in predicting the outcome of treatment will be tested in a Cox model. Stepwise elimination of non significant covariates will be undertaken and only those covariates that remain statistically significant will be retained in the model. Tests of proportionality will be undertaken using graphical (Nelson Aalen) and quantitative methods (Schoenfeld test). The data will be presented graphically using Kaplan Meier graphs. The

results of the multivariable analysis will be presented as Hazard ratios together with 95% confidence intervals and p-values generated from the model.

9.4.2 *Change in wound size*

An important secondary outcome measure is partial wound healing, which is a function of wound area and perimeter change. Care must be taken to choose an appropriate measure for this outcome, as measures such as reduction in area or percentage reduction in area usually lead to biased comparisons. It is proposed that the trial uses the linear healing measure of Gowland-Hopkins & Jamieson⁴⁴ and described in Gilman⁴⁵. This measure is defined as:

$$d = \Delta A/p_{avg}$$

where ΔA is the change in wound area between two successive visits and p_{avg} is the average of the wound perimeters measured at these two visits. 'd' will be calculated weekly after randomization to treatment.

Comparisons of the two treatment groups will be carried out in terms of d, at each of these assessments. An unpaired t test will be carried out at each assessment, to test the hypothesis that the treatment groups do not differ in terms of d, against the alternative hypothesis that the treatment groups differ in terms of d. A 95% confidence interval for the difference between treatment groups in terms of 'd' will be calculated, based on the t test results.

9.4.3 *Wound recurrence rate.*

The wound recurrence rates will be analyzed with a time to event strategy as in 9.4.1.

9.4.4 *Incidence of amputation*

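### Recurrence is not verified in healed subjects at the two follow-up contacts, and its time-to-event analysis has no rule for dating a re-opening

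*Combined protocol and SAP*

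**What the plan says.** Section 3.3.2 lists "Incidence of reoccurrence" as the third secondary endpoint. Section 7.1.2 defines it: "Recurrence is identified as an interruption in the epithelium following complete healing of the index ulcer". It adds: "If the subject does have a recurrence, this will be documented and the re-opened ulcer will be measured and recorded".

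Closure itself is checked in clinic and confirmed two weeks later, with a photograph of the closed ulcer (8.2.7). After that, 8.2.8 places one contact at 12 weeks (±2) and 8.2.9 a second 26 weeks (±2) after the first. In both, data are collected at the subject's "preference by telephone or in the clinic if attending a routine visit for wound care". Item 6 in both lists is "Digital Photograph of the open index ulcer", and 8.2.9 qualifies it further as being done where possible. Neither list has an item for inspecting a healed site, for recurrence, or for the date of re-opening.

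Table 8.1.1 differs. It marks digital photographs at both follow-up contacts with no restriction to open ulcers, and it leaves wound assessment and measurement blank at both.

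On analysis, 9.4.3 says: "The wound recurrence rates will be analyzed with a time to event strategy as in 9.4.1". Section 9.4.1 specifies a Cox model with Kaplan-Meier plots. Its censoring rule was written for healing and refers to withdrawal or loss to follow-up.

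**The concern.** A break in the epithelium has to be seen. The subjects at risk of recurrence are the healed ones. They are also the ones the follow-up sections do not require anyone to look at, because the clinic route applies only to a subject already attending for wound care and the photograph applies only to an open ulcer. In-person detection therefore depends partly on already having a wound problem. The biopsy section (8.2.5) also remarks that "most subjects in this study will be insensate in the area of the wound", so a re-opening may not be felt.

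Two things are at stake. Missed re-openings would lower the observed recurrence rates and the power to compare them. And for the re-openings that are found, the plan does not say what date enters the model. If contact dates are used, most events fall on two tied times fixed by the schedule.

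**Working it through.** **Inputs from the documents.** Healing 43% control and 64% active, 80% power, no continuity correction, nominal level 0.022 at each of three looks, 110 per arm (9.1). Contacts at 12 weeks and 26 weeks later (8.2.8, 8.2.9): 12 + 26 = 38 weeks. The documents give no recurrence rate, detection rate or power for recurrence, so those below are assumptions.

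**The plan's own figure.** n per arm = [z(1−α/2)·√(2p̄q̄) + z(0.80)·√(p₁q₁+p₂q₂)]² / (p₁−p₂)², with p̄ = 0.535.
- α = 0.05: (1.960×0.7054 + 0.842×0.6896)² / 0.0441 = 87.4, so 88.
- α = 0.022: (2.290×0.7054 + 0.842×0.6896)² / 0.0441 = 109.3, so 110.

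Both stated sizes reproduce.

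**Subjects at risk of recurrence.** 110×0.43 = 47.3 and 110×0.64 = 70.4, about 118 in all if the trial runs to 220.

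**How coarse the dates are.** With a constant hazard and assumed recurrence R by week 38, the share of recurrences falling between the two contacts is [R − (1 − (1−R)^(12/38))] / R. This is 66% for R = 20%, 63% for 40% and 58% for 60%. Most re-openings would be placed only within a 26-week interval.

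**Effect of coarse dates alone.** Simulation, 500 runs: 47 and 70 healed subjects, exponential recurrence, 40% control recurrence by week 38, true hazard ratio 0.5, all events found. Rejection is the share of runs with p < 0.05.

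| Analysis | Median HR | Rejection | Rejection if HR = 1 |
|---|---|---|---|
| Cox, exact dates | 0.49 | 53% | 4.2% |
| Cox, contact dates, Breslow ties | 0.52 | 47% | 1.6% |
| Cox, contact dates, Efron ties | 0.49 | 53% | 3.8% |
| Grouped-time complementary log-log | 0.49 | 54% | 3.8% |

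The Monte Carlo standard error of a rejection rate near 50% is √(0.25/500), about 2 points. All four methods were fitted to the same simulated data.

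**Effect of missed events.** Observed rate = detection share × true rate. With true rates of 20% and 10%, detection of 60% gives 12% and 6%, and detection of 90% gives 18% and 9%. The 10-point difference becomes 6 to 9 points, while the risk ratio stays at 2.0. Power at two-sided 0.05, with 47.3 and 70.4 at risk:

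| True rates | 100% found | 70% found | 50% found |
|---|---|---|---|
| 40% v 20% | 66% | 47% | 34% |
| 20% v 10% | 34% | 25% | 19% |
| 40% v 30% | 20% | 14% | 11% |

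In the simulation, missing 30% of events equally in both arms moved the median hazard ratio to 0.53–0.55 and cut rejection to 29–34%. The hazard ratio shifts a little although the risk ratio does not. A true ratio of 0.5 gives 40% and 1 − √0.6 = 22.5%. At 70% detection these become 28% and 15.8%, and ln(0.842)/ln(0.72) = 0.52.

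**The case against.** Recurrence does not rest on one unprompted report. The Cardiff Wound Impact Schedule is due at both contacts, and its form (Appendix I) has a box for wound status, healed or not. Adverse events are recorded at both contacts. Section 3.3.3 covers wound worsening and asks for duration, which implies an onset date, and 7.2.8 lists fresh areas of breakdown. The economic assessment takes a dressing history. A re-opened ulcer is an open ulcer, so item 6 does cover it. Measurements come from the central assessor's reading of photographs (7.1.1), so a blank assessment row does not prevent measuring an ulcer that is photographed.

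Much of this stands. What remains is that at a telephone contact these routes are all self-report, and none asks specifically about the healed index site. A call without a photograph also cannot yield the measurement that 7.1.2 requires.

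A reader might infer more than the documents support:
- *That follow-up is by telephone only.* It is telephone or clinic, by preference.
- *That only open ulcers are ever photographed.* That is the text of 8.2.8 and 8.2.9. Table 8.1.1 says otherwise, and the two must be reconciled.
- *That under-counting is established.* It is likely, but no figure in the documents sizes it. The remark on sensation explains why anaesthesia is not routine for an optional biopsy set, and a subject or caregiver can see a break without the subject feeling it.
- *That a time-to-event analysis is impossible.* The simulation shows otherwise. Nor does 9.4.3 say that contact dates will serve as event times; it gives no rule.
- *That a stated durability objective fails.* The synopsis objectives are efficacy, safety and economic benefit. Recurrence is one of seven secondary endpoints, with no power claim.

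**Conclusion.** The point holds in limited form. Ascertainment of recurrence in healed subjects is unverified and probably incomplete, and its time-to-event analysis is under-specified.

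Using contact dates coarsens the analysis. On the assumed rates the worst option examined, Breslow ties, costs about 6 points of rejection (53% to 47%) and moves the median hazard ratio from 0.49 to 0.52; Efron ties or a grouped-time model lose essentially nothing. Incomplete detection could cost more, for example 66% power down to 47% at 70% detection for 40% v 20%, but those rates and detection shares are assumptions. Equal misses between arms, which is plausible if blinding holds, would lower both rates and their difference and leave the risk ratio roughly unchanged. The primary endpoint is not affected.

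This is more than a missing detail. Following 8.2.8 and 8.2.9 as written leaves healed sites unchecked, and onset dates or closed-site images not collected during follow-up cannot be reliably recovered later.

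**What to change.** 1. Reconcile 8.2.8 and 8.2.9 with table 8.1.1, so that item 6 in both lists calls for a digital photograph of the index ulcer site, open or closed.
2. At telephone contacts, ask the subject or caregiver to look at the site during the call and send a photograph where possible.
3. Add to the CRF an index-site recurrence item (yes/no) with the date last known closed and the date first noticed open.
4. In 9.4.3, specify a grouped-time or interval-censored model, or Cox with Efron ties, and report the proportion recurred by each contact.

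The cost is two added CRF items, revised wording in two sections and a changed analysis paragraph, with no extra visits. Some telephone subjects will not supply a photograph, and pictures taken at home fall outside the site tablet process in 7.1.1. Checking reports against outside wound-care records would strengthen the endpoint but adds staff work, so it is optional.

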8.2.10 Definition of the End of Trial

For the purposes of notifying the IRB/Ethics Committee and the Competent Authorities, the end of the trial is defined as completion of the final 38 week follow-up on the final subject remaining in the trial.

8.2.11 Premature Termination of the Trial

If AOTI Ltd. or the principal investigator discovers conditions arising during the trial which indicate that the trial should be halted, it must be terminated after appropriate consultation between AOTI Ltd. and the principal investigator. Conditions that may warrant termination include, but are not limited to:

1. The discovery of an unexpected, significant or unacceptable risk to the subjects enrolled in the trial.
2. Failure of the investigator to enter subjects into the study at an

acceptable rate.

3. Insufficient adherence to the protocol.
4. If study data at interim analysis indicates that treatment with TWO2 therapy is of no clear benefit to diabetic patients with diabetic foot ulcers.

If the trial is prematurely terminated or suspended for any reason, the investigator and subjects will be informed promptly. Appropriate therapy and follow up for subjects will be assured.

- The investigator must notify the IRB/Ethics Committee of any premature termination of the trial, within 15 days, using the "Declaration of End of Clinical Trial" form available from the EudraCT/and other relevant websites.
- AOTI Ltd. will notify the Regulatory Authorities within 15 days using the same process.

8.2.12 *Subjects Lost-to-follow-up*

Every effort should be made for all subjects enrolled in this study to complete all study visits and assessments including the follow-up phase. A minimum of three (3) documented telephone calls will be made to any subject who does not return for scheduled treatment or follow up visits. Should the telephone calls be unsuccessful in contacting the subject, a certified letter will be sent. Only after a minimum of four (4) attempts to get the subject to return to the clinic, will the subject be considered "lost-to-follow-up".

If the subject has to stay in the hospital for another medical condition or because of the diabetic ulcer, all reasonable efforts will be undertaken to continue the trial treatment on discharge, if the hospitalization is no longer than 4 weeks.

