3. OVERALL STUDY DESIGN AND PLAN

3.1. Overview

This is a multi-center trial, to be conducted at up to 30 sites in the United States, Canada, and Europe.

Inclusion criteria for participation in the trial include the presence of documented diabetes (Type I or II) with non-healing, full-thickness, University of Texas Classification of Diabetic Foot Ulcers Grade 1 and 2 diabetic foot ulcers of at least 4 weeks duration, but not greater than 1 year, measuring 1cm² or greater and less than or equal to 20 cm².

Subjects will be asked to sign a written informed consent form, approved by an IRB/Ethics Committee, prior to participation in the trial at the screening study visit. Each subject will be assigned a Subject Identification Number, which will be used for identification purposes in order to ensure subject confidentiality. All subject data held on the study Sponsor's database will be anonymised and identifiable only by Subject Identification Number.

Those who continue to meet all of the eligibility criteria after the 2 week run-in period will be enrolled into the trial and randomized to one of two treatment arms: TWO₂ therapy or, Control therapy.

In this trial a maximum of 220 subjects will be recruited. A Group Sequential Designs (GSD) with interims analyses after one third and two third recruited subjects has been chosen that will allow the trial to be stopped if TWO₂ therapy is obviously better than control therapy.

Subjects will be recruited as outpatients in participating wound care centers and clinics. At the screening visit the informed consent document must be signed, the wound will be measured and the subject will receive a standardized off-loading device for weight bearing wounds. The subject will from then on, be treated with predefined dressings used in the total treatment phase of the study.

A diary card will be given to every subject. Subjects will be instructed on keeping the simple diary card to record the use of the TWO₂ or control device, dressing changes and to collect data for health economic analysis. A study ID card will also function as an alert to other providers of participation in a clinical study (example Appendix I).

After a run-in period of 2 weeks the subject will be randomized into the study if the wound-size reduction is less than 30% of the initial measurement and all other inclusion and exclusion criteria are met.

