5.1. Identification numbers

Each subject who has signed a written IRB/Ethics Committee approved Informed Consent Form will receive a unique subject ID number. The number will have 6 digits. The first two numbers will be the country code, the next two digits will define the center and the last two digits will be consecutive screened subjects in this center.

After all baseline medical data is recorded and the wound is documented at the 2 week baseline/randomization visit, the subject's number will become the subject identification number (Subject ID) for the remainder for the study. The investigator will not know to which treatment arm the subject is allocated throughout the trial.

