9.6 Independent Data Monitoring Committee

As suggested by international guidelines on data monitoring committees, an independent Data Monitoring Committee (DMC) will be formed to decide whether the predefined criteria for early stopping of the trial are met.^{46,47} The DMC will meet at the interim analysis to be performed after 73 and 146 subjects and at the end of study. In the event of new unanticipated and related adverse effects being reported, the DMC will convene for an unscheduled meeting and will determine at that time the need for additional review and or action.

The Data Monitoring Committee will consist of three to five independent experts outside of the study group. These members:

- will not be involved in the conduct of the clinical trial
- will not have any financial interest in the outcome of the study
- will have no planned authorship in publications on study results
- will not serve in parallel on the DMC of a clinical trial with diabetic patients with a different sponsor

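### Section 8.2.11 item 4 lets the sponsor and principal investigator stop the trial for lack of benefit on interim data, with no threshold and no DMC role, in conflict with section 9.6

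*Combined protocol and SAP*

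**What the plan says.** Section 8.2.11 opens: "If AOTI Ltd. or the principal investigator discovers conditions arising during the trial which indicate that the trial should be halted", and continues: "it must be terminated after appropriate consultation between AOTI Ltd. and the principal investigator". Four example conditions follow, introduced as ones that may warrant termination. The fourth is: "If study data at interim analysis indicates that treatment with TWO2 therapy is of no clear benefit". No numeric limit, look or DMC recommendation is attached to it, and the section does not mention the DMC.

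Section 9.6 says that an independent DMC "will be formed to decide whether the predefined criteria for early stopping of the trial are met". On timing it says: "The DMC will meet at the interim analysis to be performed after 73 and 146 subjects and at the end of study".

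The only numeric stopping criterion is in section 9.1: a Pocock boundary of p<0.022 at each of three analyses. Section 3.1 describes the interim looks as there to "allow the trial to be stopped if TWO₂ therapy is obviously better than control therapy". It mentions no stop for lack of benefit.

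On blinding, section 5.1 says: "The investigator will not know to which treatment arm the subject is allocated throughout the trial". Section 5 lists the reading centre, investigators and monitors as unaware of allocation. The sponsor is not on that list, and it acts as the randomization centre. No section says who runs the interim comparison or who may see results by arm.

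**The concern.** Two sections assign action on the same interim data to different parties. Section 9.6 confines the DMC to criteria set in advance, and lack of benefit is not one of them. Section 8.2.11 gives a lack-of-benefit stop to the sponsor and principal investigator under a phrase with no stated meaning.

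Two things are at stake. The first is the integrity of the remaining trial. If the parties who run it, and who supervise clinical judgements of closure (7.1.1), learn the trend by arm and the trial goes on, conduct and assessment after that point can be influenced. The second is power. At one third of the sample, an unimpressive result is common even when the planned effect is real, so a loosely read futility clause can end a trial of a working device.

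**Working it through.** **Inputs.** Control 43%, active 64%, two-sided test, 80% power, 110 per arm, p<0.022 per look (9.1). Uncorrected chi-squared at the interims (9.3). Looks at 73 and 146 of 220 (9.6), taken as 37/36, 73/73 and 110/110 per arm. All subjects at a look are assumed to have a 12-week outcome, as in the synopsis.

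**1. The plan's own figures.** With p̄ = 0.535, 2p̄(1−p̄) = 0.49755 and the sum of the two arm variances 0.43×0.57 + 0.64×0.36 = 0.4755:

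n per arm = [z(1−α/2)·√0.49755 + 0.8416·√0.4755]² / 0.21²

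- α = 0.05: (1.960×0.7054 + 0.8416×0.6896)² / 0.0441 = 87.4, so 88. This matches.
- α = 0.022: (2.290×0.7054 + 0.8416×0.6896)² / 0.0441 = 109.3, so 110. This matches.

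Three looks at nominal 0.022 give an overall two-sided error of 0.0499. The efficacy design is sound as stated.

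**2. Who decides, side by side.**

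| | 8.2.11 item 4 | 9.6 with 9.1 and 3.1 |
|---|---|---|
| Decision-maker | Sponsor and principal investigator | Independent DMC |
| Ground | No clear benefit | Predefined criteria; only p<0.022 exists |
| Threshold | None | 0.022 |
| Direction | Lack of benefit | Benefit only (3.1) |

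**3. Power without a lack-of-benefit stop.** Simulation of the three-look design under 43% v 64% gives 84.3%: about 29.5% of trials cross at look 1, 35.0% at look 2 and 19.7% at the end. This exceeds 80% because 110 per arm already gives 80.3% at the final test alone.

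**4. Power if item 4 is applied at the first look.** Overall power = P(cross at look 1) + P(not stopped at look 1 and cross later). Stop probabilities are exact binomial at 37 v 36; power is simulated. The planned effect is true throughout.

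| Reading of the phrase at look 1 | Effective trials stopped | Overall power |
|---|---|---|
| Difference zero or negative | 3% | 83% |
| Difference under 5 points | 9% | 80.5% |
| Difference under 10 points | 19% | 74% |
| p>0.05 | 53% | 46% |
| p>0.022 | 70% | 30% |

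Three of the five readings put power below the stated 80%, and a fourth leaves almost no margin.

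**5. An example of a defined rule.** Conditional power at the second look under the planned effect:

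CP = Φ{[z₂√t + θ(1−t) − 2.290] / √(1−t)}, with t = 146/220 = 0.664 and θ = 0.21/√(0.4755/110) = 3.194.

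Setting CP = 10% (Φ⁻¹ = −1.282) gives z₂ = (2.290 − 3.194×0.336 − 1.282×0.580)/0.815 = 0.58. That is an observed difference of about 0.58×√(0.49755/73) = 0.048, or 5 points. Stopping below this value leaves power at 84.2% against 84.3%, and stops about 70% of trials in which both arms heal at 43%.

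**The case against.** The two sections can be read together. The DMC meets at each interim, reports a conclusion, and the sponsor and principal investigator then consult on termination. Item 4 is discretionary, and a sponsor normally keeps authority to end its own trial. High rates of non-significance at one third of the sample are ordinary and are not a defect in themselves. The choice of a futility rule is a matter of preference, and having none is acceptable.

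Much of this stands, and it limits what can be said. A reader might infer any of four stronger points:

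- *Item 4 requires unblinded results to leave the DMC.* No passage says that the sponsor or an investigator sees results by arm. The documents are silent on data flow. What can be said is that they allow it and write no other route.
- *It breaks the blind.* Totals by arm do not reveal any subject's allocation. The control device looks and acts the same (6.2), no device treatment is given at study centers (3.1), and a blinded central assessor also reviews photographs (3.1, 7.1.1). The exposure is operational bias from knowing the trend.
- *Power falls to 46%.* That is one reading in a range from 30% to 83%. The protocol never uses 0.05 as an interim level and never equates non-significance with no benefit.
- *Type I error rises.* Stopping for lack of benefit does not raise it.

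What the objection does not remove is the conflict. Reading the sections together needs a DMC recommendation on lack of benefit, but section 9.6 limits the DMC to predefined criteria and none covers it.

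**Conclusion.** The concern holds as a conflict over who acts on between-arm data, and as an undefined stopping ground. It should be corrected before the first interim analysis. As written, comparative results may reach the sponsor and principal investigator while the trial continues, with a risk of operational bias. Applied at the first look, item 4 costs anywhere from about 1 point of power (84.3% to 83%) to more than 50 points (to 30%), depending on a threshold that the plan does not give. The stated 80% is therefore not assured.

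The figures rest on 43% v 64%, complete 12-week outcomes for 73 subjects, and use of the clause at the first look only. Section 9.1 times the looks by recruitment rather than by completed outcomes, and fewer outcomes would make the first look weaker. How often the clause would be invoked cannot be known from the documents.

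**What to change.** 1. Amend 8.2.11 item 4 and 9.6 so that termination for lack of benefit follows only a DMC recommendation. The sponsor and investigators receive *continue* or *stop*, and no results by arm.
2. Then choose one of two courses. Either delete item 4, which agrees with the benefit-only description in 3.1, or replace the phrase with a predefined non-binding rule that the DMC applies. Conditional power below 10% at the second look under 43% v 64% is one reasonable example among several. If a rule is kept, add it to 9.1 and 3.1.
3. State in 9.6 that the interim comparison is prepared for the DMC separately from sponsor staff who run the trial. This is needed because the sponsor is the randomization centre and is not listed as blind (section 5), so rewording item 4 alone would not secure the separation.

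Items 1 to 3 of 8.2.11 and the p<0.022 boundary stay as they are. The cost is wording in a few sections and a separate preparer for the interim analyses. The example rule costs about 0.1 point of power. Because it is non-binding and the efficacy boundary is unchanged, it does not raise type I error.
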